4.7 Study Assessment Time Points

The study consists of 8 protocol-specified visits which will be assessed as nominal visits from an analysis perspective:

- Visit 1, Screening Visit (Day -14 to -7)
- Visit 2, Baseline (Day 1): Subjects will be randomized after eligibility has been confirmed, study drug/placebo dispensed.
- Visit 3 (Day 14 ± 2)
- Visit 4 (Day 28 ± 2)
- Visit 5 (Day 56 ± 2)
- Visit 6 – End of Treatment (EOT) (Day 84 ± 2)
- Visit 7 (Day 98 ± 3 or 14 days after Early Termination)
- Safety Follow-Up (Day 114 ± 2 or 30 days after Early Termination): a documented phone call to record AEs and concomitant medications (CMs).
- Early termination: In cases of early termination, if a subject has received at least 1 dose (400 mg) of AKST4290 or placebo, the site should try to perform all assessments scheduled at the Visit 6 - EOT visit as well as the subsequent follow up visits unless the subject has withdrawn consent.

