5.2.2 Modified Intention-to-Treat (mITT)/Evaluable Population

The mITT/evaluable population will be a subset of the ITT population that only includes subjects with non-missing baseline and Week 12 (Day 84) values for off-medication motor function as measured by the MDS-UPDRS Part 3. Analysis will be done according to the treatment subjects were randomized to.

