5.6 Methods for Handling Missing Data

In order to minimize missing data, every effort will be made to obtain required data for all randomized subjects at each scheduled evaluation. However, in the event that more than 5% of data are missing, imputation methods will be used for analysis of the primary endpoint only. The imputation will be carried out in SAS version 9.4 or later using PROC MI.

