A mixed-effect model for repeated measures (MMRM) will be employed to analyze the change from baseline scores at each visit over time up to Week 12. The model will include the fixed effects of treatment (stratified, by sex), baseline of the endpoint, visit, and treatment by visit interaction. An unstructured covariance structure will be used to model the within subject error. Least-square (LS) means, standard error (SE), and 95% CI of the LS mean will be provided for each treatment arm at each visit. The unadjusted mean change from baseline, and the difference in LS means between treatment arms and 95% CI of the difference will also be calculated. P-value for testing whether the difference is equal to zero will be provided. The p-value at Week 12 will be compared against the alpha significance level of 0.1.

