5.7.1.1 Sensitivity Analyses

The main analysis of the primary endpoint using the above MMRM will use all available data. To check the robustness of the results, the following sensitivity analyses will be performed:

FM DM015.1
Statistical Analysis Plan
AKST4290-211

Rev B
Page 18 of 30

- Analysis of covariance (ANCOVA) model on the observed change from baseline value at Week 12. The model includes treatment as the fixed effect and baseline of the endpoint as a covariate.
- The same MMRM model on data from the PP subjects.
- The same MMRM model on data from the ITT subjects.
- Depending on the status of missing data among the mITT population, multiple imputations may be employed to handle missing data and apply the MMRM on the imputed datasets. See Methods for Handling Missing Data section (section 5.6) for details on imputation methods.

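### The multiple-imputation sensitivity analysis is tied to the mITT, where no Week 12 score can be missing, so it cannot test robustness to missing primary-endpoint data; the base of its 5% trigger is also left open

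*SAP*

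**What the plan says.** - **Population of the main analysis.** Section 5.7.1 puts the primary analysis on the mITT. Section 5.2.2 says this population "only includes subjects with non-missing baseline and Week 12 (Day 84) values" of the off-medication Part 3 score.
- **Visits in the model.** Off-medication Part 3 is scheduled at baseline and Weeks 4, 12 and 14. The MMRM in 5.7.1 runs up to Week 12, so its outcomes are Weeks 4 and 12. Results are reported at both: "Least-square (LS) means, standard error (SE), and 95% CI of the LS mean will be provided for each treatment arm at each visit".
- **Imputation as a sensitivity analysis.** Section 5.7.1.1, fourth bullet: "Depending on the status of missing data among the mITT population, multiple imputations may be employed to handle missing data". The MMRM is then applied to the imputed data. For the method the bullet says "See Methods for Handling Missing Data section (section 5.6) for details on imputation methods".
- **Trigger.** Section 5.6 first sets the aim of obtaining "required data for all randomized subjects at each scheduled evaluation". It then says that "in the event that more than 5% of data are missing, imputation methods will be used for analysis of the primary endpoint only". On method it names only PROC MI.
- **The other route to subjects without Week 12.** Section 5.7.1.1, third bullet: "The same MMRM model on data from the ITT subjects".
- **Numbers.** Section 4.4 plans about 120 randomized subjects, to yield about 108 evaluable.

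**The concern.** A missing-data sensitivity analysis should ask what happens to the Week 12 comparison if the subjects without a Week 12 score differ from those who have one. Here the imputation is conditioned on a population from which exactly those subjects have been removed. Run as written, it would appear in the report as a robustness check on missing data while imputing no primary-endpoint value.

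The trigger adds a second difficulty. Section 5.6 leans towards randomized subjects, 5.7.1.1 names the mITT, and neither says whether the 5% is counted at Week 12 alone or over all modelled visits. The same data could call for the analysis or rule it out.

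**Working it through.** **1. Reproduce the planned numbers.** 108 / (1 − 0.10) = 120, which matches section 4.4. The 10% is inferred as 1 − 108/120 = 0.10; the SAP does not state it. About 120 − 108 = 12 subjects are expected outside the mITT. Below I assume that all 12 lack Week 12 rather than baseline.

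**2. What can be imputed in the mITT.** Of the three Part 3 scores that the model uses:
- Baseline: never missing in the mITT (5.2.2).
- Week 12: never missing in the mITT (5.2.2).
- Week 4: may be missing.

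The number of imputable Week 12 values is therefore 0 by definition.

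**3. Can filling Week 4 still matter for Week 12?** Hardly. Every mITT subject contributes an observed Week 12 change. A missing Week 4 value can reach the Week 12 contrast only indirectly, through the sex and baseline coefficients that the model shares across visits and through the estimated covariance.

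A simulation with assumed inputs illustrates this: 150 trials of 120 subjects, SDs of 9 to 10, within-subject correlation about 0.54, true Week 12 difference −3, 12 dropouts concentrated among treated subjects with poor outcomes, and 6 Week 4 scores missing in the mITT. The mean Week 12 difference was −3.12 with full data, −5.66 in the mITT, −5.66 in the mITT after imputation, and −4.97 in the ITT MMRM. Imputation moved the mITT estimate by 0.008 points on average (largest 0.05). The dropout pattern is deliberately adverse. The direction is informative; the size is not a forecast.

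**4. The 5% trigger under each reading.** The rule requires more than 5%. The pooled ITT range runs from all 12 subjects having Week 4 to none having it, with no other Week 4 gaps.

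| Reading | Smallest count that fires | At planned numbers |
|---|---|---|
| ITT, Week 12 | 7/120 = 5.8% | 12/120 = 10%: fires |
| ITT, Weeks 4 and 12 pooled | 13/240 = 5.4% | 12/240 = 5.0% (does not fire) to 24/240 = 10% (fires) |
| mITT, Week 12 | none | 0/108 = 0%: cannot fire |
| mITT, Week 4 | 6/108 = 5.6% | depends on Week 4 gaps |
| mITT, Weeks 4 and 12 pooled | 11/216 = 5.1% | depends on Week 4 gaps |

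**5. Would moving the imputation to the ITT be enough?** Under MAR it uses essentially the same model and data as the ITT MMRM, so the two should nearly agree. In a second simulation they differed by 0.07 to 0.12 points, or 4 to 7% of a standard error of 1.6 to 1.7. It used 960 trials of 60 per arm, SD of change 9, Week 4 to Week 12 residual correlation 0.4 to 0.8, and 6 per arm without Week 12, all assumed. With 20 imputations and about 8% missing information (assumed), Monte Carlo error alone is about √(0.08 × 1.65² / 20) = 0.10 points.

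A departure from MAR does add information. If 6 of 60 active-arm subjects are imputed with a shift delta, the difference moves by (6/60) × delta = 0.10 × delta. At delta = 5, an illustrative value, that is 0.5 points, or 0.5/1.65 = about 30% of the assumed standard error.

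**The case against.** The strongest reply is that the plan already reaches subjects without Week 12 through the ITT MMRM, so little is lost. Much of this stands: a reader might infer that missing Week 12 data go wholly unaddressed, and that would be wrong. But the ITT MMRM takes in only those with a Week 4 score, since a subject with no post-baseline score contributes nothing. It also assumes MAR, and no listed analysis relaxes that assumption.

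A second reply is that the mITT imputation is not empty. That is correct: Week 4 is a modelled and reported outcome. It is not the primary time point, however.

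A third is that the mITT wording sets only the condition, and that the imputation itself could be done more widely. Even so, the condition would watch a population whose Week 12 missingness is always zero.

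Some stronger readings are tempting but do not hold:
- *Will* in 5.6 against *may* in 5.7.1.1 is not a contradiction in itself. A conditional *may* that refers to 5.6 is compatible with *will* once the trigger is met. The wording is untidy.
- Imputation for the primary endpoint in 5.6 and imputation as a sensitivity analysis in 5.7.1.1 do not conflict. A sensitivity analysis of the primary endpoint is an analysis of that endpoint.
- Section 5.6 is not wholly silent on population, because its preceding sentence speaks of all randomized subjects. The fault is that this differs from the mITT and that no denominator is fixed.
- The COVID-19 note in 4.8 permits missed assessments and anticipates more deviations. It does not predict missing Part 3 scores.
- The brief reference to PROC MI is thin detail, not an error.

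**Conclusion.** The point stands in this form: as written, the imputation bullet cannot test robustness to missing primary-endpoint data, and its trigger has no agreed base. The first part follows from the SAP's own definitions and needs no assumption. The second depends on about 12 subjects lacking Week 12, which is inferred from 120 and 108. On that count the missing share is 10%, 5.0% to 10%, or 0%, according to the reading.

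A reader might infer that the primary result is compromised. The documents do not support that: the imputation is listed as a sensitivity analysis, and the main MMRM is the same with or without it. The simulated figures rest on inputs that the SAP does not give and show direction only. This should be corrected, but the main analysis does not depend on it.

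**What to change.** - **5.7.1.1, fourth bullet:** change mITT to ITT, and align *may* with the *will* of 5.6.
- **5.6:** define the trigger as more than 5% of randomized subjects without a Week 12 off-medication Part 3 score, or drop the trigger and always run the analysis. Impute Week 12 from arm, sex, baseline and Week 4, imputing Week 4 first where it is also missing.
- **Departure from MAR:** because MAR imputation in the ITT nearly repeats the ITT MMRM, run it with a delta-adjusted (tipping-point) or reference-based version. Without this the edit repairs the text but adds little information.
- **Count:** section 4.7 says that after early termination "the site should try to perform all assessments scheduled at the Visit 6 - EOT visit". It would help to state whether such a score counts as Week 12, since this affects both mITT membership and the trigger count.
- **Timing:** settle the choice, including the deltas or the reference rule, before unblinding. Section 4.5.2 places general unblinding after database lock, so this can be done blind.

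Keep the other three sensitivity analyses. The cost is a few lines of SAP text, modest programming and one more supportive result to report. No new data are needed, and the primary result does not change.

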5.7.2 Secondary Efficacy Endpoints

Secondary efficacy endpoints will be analyzed using the mITT/Evaluable, ITT, and PP populations. Please see Safety Analysis section (Section 5.8) for information regarding analysis of safety endpoints.

Secondary efficacy endpoints include the following:

Change from Baseline (Day 1) in clinical function, motor function, and activities of daily living at Week 12 (Day 84) during the on-medication state as assessed by:

- MDS-UPDRS Parts 1-4
- Montreal Cognitive Assessment
- Schwab and England Activities of Daily Living Scale
- Clinical Impression of Severity Index – PD
- PD Quality of Life Questionnaire-39
- Sheehan-Suicidality Tracking Scale
- 10-meter timed walk (will also be assessed in the off-medication state)
- Hauser 3-Day Patient Diary

5.7.2.1 MDS-UPDRS Parts 1-4

The MDS-UPDRS Parts 1-4 is administered in the on-medication state at Baseline and Weeks 2, 4, 8, 12, and 14. The scores for each section (i.e. sum of corresponding items for each section) will be summarized descriptively at each scheduled visit. Additionally, the difference in the MDS-UPDRS Part 3 between the on-medication and off-medication state will be reported.

To evaluate change from baseline, the same MMRM model used to evaluate the primary endpoint will be employed to produce LS means, SE, and 95% CIs of the LS means for each treatment arm at each scheduled visit. The unadjusted mean change from baseline, and the difference in LS

means between treatment arms and 95% CI of the difference will also be calculated.

5.7.2.2 Montreal Cognitive Assessment

The MoCA (Nasreddine, 2005) is a screening test used to assess attention and concentration, executive function, memory, language, visuo-constructional skills, conceptual thinking, calculations, and orientation. The total possible score is 30 points with a score of 26 or more considered normal.

The MoCA is administered at Baseline and Week 12 in the on-medication state. The total score will be summarized at each scheduled time point. To evaluate change from baseline, an analysis of covariance (ANCOVA) model will be used to produce the LS mean, SE, and 95% CI of the LS means for each treatment arm. The unadjusted mean change from baseline, and the difference in LS means between treatment arms and 95% CI of the difference will also be calculated. A summary of each cognitive domain will be provided as well.

5.7.2.3 Schwab and England Activities of Daily Living Scale

The SE-ADL evaluates patients' perceptions of global functional capacity and dependence (Schwab, 1968). Scoring is expressed in terms of percentage, in 10 steps from 100 to 0 (100%, normal status; 0%, bedridden with impaired vegetative functions), so that the lower the score, the worse the functional status.

Scores are collected at Baseline, and Weeks 2, 4, 8, 12, and 14. Scores will be summarized descriptively at each scheduled time point (i.e. n, %) by treatment group. A Generalized Estimating Equations (GEE) for alternating logistic regression (ALR) with an exchangeable working correlation structure will be employed to analyze change from baseline. The model will include the fixed effects of treatment, baseline of the endpoint, visit, and treatment by visit interaction. The common odds ratio and 95% CI for odds of higher versus lower SE-ADL scores between treatment groups will be presented. Mean scores at each timepoint, and change from baseline, will also be presented.

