4.2 Treatment Assignment and Dose Regimen

A subject number will be assigned once the subject has signed the informed consent form. Enrolled subjects that have met all eligibility criteria will be randomized to AKST4290 (Arm 1: active dosing) or placebo (Arm 2: placebo dosing). The study drug will be self-administered orally b.i.d. (2 x 200 mg per dose), approximately 12 hours

apart, for a total daily dose of 800 mg. Subjects will receive study drug or placebo for a total of 12 weeks, followed by 4 weeks of follow-up.

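### The single SE-ADL odds ratio is not tied to the declared Week 12 endpoint, and the visits that enter its model are not stated

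*SAP*

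**What the plan says.** Sections 3.2 and 5.7.2 of the SAP list SE-ADL among the secondary efficacy endpoints, defined as "Change from Baseline (Day 1) in clinical function, motor function, and activities of daily living at Week 12 (Day 84) during the on-medication state".

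Section 5.7.2.3 gives the visit schedule: "Scores are collected at Baseline, and Weeks 2, 4, 8, 12, and 14". It specifies the method: "A Generalized Estimating Equations (GEE) for alternating logistic regression (ALR) with an exchangeable working correlation structure will be employed to analyze change from baseline". The terms are listed as follows: "The model will include the fixed effects of treatment, baseline of the endpoint, visit, and treatment by visit interaction". The effect to be reported is: "The common odds ratio and 95% CI for odds of higher versus lower SE-ADL scores between treatment groups will be presented". The section adds: "Mean scores at each timepoint, and change from baseline, will also be presented".

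On the duration of treatment, section 4.2 states: "Subjects will receive study drug or placebo for a total of 12 weeks, followed by 4 weeks of follow-up".

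**The concern.** The endpoint has a time point and the reported effect does not. Once treatment is allowed to interact with visit, there is no single treatment odds ratio until someone names a visit or a weighting over visits. Section 5.7.2.3 does neither, and it does not say which of the collected visits enter the model. Week 14, two weeks after the planned end of treatment, is therefore not excluded.

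This odds ratio is the only between-arm estimate specified for SE-ADL. The other outputs (counts and percentages, mean scores, change from baseline) are given by visit, but no treatment difference is named for them. Two programmers could each follow the section faithfully and report different numbers for a declared endpoint, and neither number need be the Week 12 effect.

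A smaller ambiguity concerns the response. The model is said to analyse change from baseline, while the odds ratio is for higher versus lower scores.

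**Working it through.** The SAP states no SE-ADL odds ratio, effect size or power, so there is no figure to reproduce. The check compares the text across sections and then uses arithmetic on assumed values.

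**1. The text, side by side**

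| Item | SE-ADL (5.7.2.3) | Comparison |
|---|---|---|
| Time point of the endpoint | None in this section | Week 12 (3.2, 5.7.2) |
| Last visit in the model | Not stated; scores collected to Week 14 | Primary MMRM limited to visits through Week 12 (5.7.1) |
| Model-based output | One odds ratio, no visit named | CISI-PD and PDQ-39, on the same visit schedule: LS means at each scheduled visit, and a treatment difference with 95% CI (5.7.2.4, 5.7.2.5) |

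CISI-PD and PDQ-39 reuse the primary MMRM and so take over its Week 12 limit. SE-ADL has its own model and takes over nothing.

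**2. What the model contains**

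The treatment effect at visit v is

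log OR(v) = b_trt + b_trt×v,

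with b_trt×v = 0 at the reference visit. With five post-baseline visits there are five odds ratios. A single figure without a visit could be:

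- (a) an average of log OR(v) over the modelled visits; or
- (b) exp(b_trt), the odds ratio at whichever visit the coding makes the reference.

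The Week 12 effect is exp(b_trt + b_trt×12).

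**3. Illustration**

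Assumed, not from the SAP: an odds ratio of 2.00 at Week 12, so log OR = 0.693. In the growing-effect rows log OR(v) = 0.693 × v/12 through Week 12, which gives 0.116, 0.231, 0.462 and 0.693 at Weeks 2, 4, 8 and 12 (odds ratios 1.12, 1.26, 1.59, 2.00). The sum is 1.502. Averages weight visits equally.

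| Assumed pattern | OR at Week 14 | Five-visit average | Average through Week 12 | exp(b_trt), Week 2 reference | exp(b_trt), Week 14 reference |
|---|---|---|---|---|---|
| Constant effect | 2.00 | 2.00 | 2.00 | 2.00 | 2.00 |
| Growing, sustained | 2.00 | 1.55 | 1.46 | 1.12 | 2.00 |
| Growing, half lost | 1.41 | 1.45 | 1.46 | 1.12 | 1.41 |
| Growing, fully lost | 1.00 | 1.35 | 1.46 | 1.12 | 1.00 |

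For example, in the last row the five-visit average is exp((1.502 + 0)/5) = exp(0.300) = 1.35. The average through Week 12 in the three growing rows is exp(1.502/4) = exp(0.375) = 1.46.

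The explicit Week 12 contrast returns 2.00 in every row. The discrepancy is nil under a constant effect. It can also be nil by coding: with a sustained effect, the coefficient at a Week 14 reference happens to equal the Week 12 value. In the other cases it depends on a choice the SAP does not make. Excluding Week 14 alone does not cure it, as the average through Week 12 shows.

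**The case against.** **The word "common".** For an ordinal scale, a common odds ratio for higher versus lower scores ordinarily means common across the score cut-points, as in a proportional-odds model. That is probably what is meant, and nothing in the section says the estimate is pooled over visits. This stands. It does not supply the missing visit, because under this reading there is still one odds ratio for each visit in the model.

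**Week 14.** A reader might infer that Week 14 is in the model and that the result would be an off-treatment contrast. The SAP does not support this. The section lists Week 14 as a collection visit, and similar lists appear for endpoints whose MMRM stops at Week 12. An off-treatment result would need Week 14 to be modelled, Week 14 to be the reference level, and the bare coefficient to be reported. None of these is stated. What can be said is that Week 14 is not excluded.

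**Whether the model can answer the question.** A reader might also conclude that the analysis cannot estimate the Week 12 effect. It can, by a contrast on the model as written. The endpoint definition makes that contrast the natural intention, but the section does not ask for it.

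**Change versus score.** Because the model adjusts for baseline, a model of the score is a reasonable way to address change. The wording is loose, but it has not been shown to alter a result.

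**Size.** The illustrative odds ratios are assumptions, and one of the four patterns shows no discrepancy under any reading.

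**Conclusion.** The point holds as a specification gap. The reported SE-ADL odds ratio is not tied to Week 12, and the visits in its model are not stated. A literal reading gives a figure that is guaranteed to equal the Week 12 effect only if the treatment effect is constant over visits, which the interaction term deliberately does not assume, or if Week 12 is the reference visit. Otherwise agreement is coincidence.

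The size of any discrepancy cannot be drawn from the SAP and ranges from none upward. The illustrated values rest wholly on the assumed Week 12 odds ratio of 2.00, the assumed time patterns and equal visit weights.

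Severity is minor. SE-ADL is one of eight listed secondary efficacy measures, no p-value or alpha is named for it, and descriptive results at Week 12 will be presented. The gap still merits correction because this is the only treatment comparison specified for the endpoint.

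**What to change.** Amend section 5.7.2.3 to state that:

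- the response is the ordinal SE-ADL score at post-baseline visits through Week 12, adjusted for the baseline score;
- the reported effect is the cumulative odds ratio for treatment at Week 12, common across score cut-points, with its 95% CI, obtained by an explicit contrast of the treatment and treatment-by-visit terms;
- odds ratios at earlier visits are supportive, and Week 14 scores are summarised descriptively.

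The cost is a few sentences of SAP text and one contrast statement in the program. The Week 12 interval will be somewhat wider than one for an average over all visits. No data collection changes. The amendment should be made before the blind is broken, so that the choice of visit is not open to influence from the results.
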